## **Auricular Percutaneous Electrical Nerve Field Stimulation for Postoperative Pain Control in Adults**

### **Study Protocol**

#### **Inclusion Criteria**

- ≥ 18 years of age
- Able to independently consent to participate
- Plans for elective laparoscopic or open colectomy or proctectomy with or without ostomy

#### **Exclusion Criteria**

- History of chronic pain disorder (requiring continuous narcotic and/or NSAID use in the week prior to surgery), or active opiate abuse
- Need for emergent procedure, regional anesthesia (does not include escalation of medical management of pain), admission to ICU
- Prolonged postoperative intubation
- Use of intraoperative ketamine or lidocaine drips
- Refusal to receive follow-up phone calls
- Tape allergy/sensitivity
- Latex allergy
- Active pregnancy
- History of seizures
- History of cerebral aneurysm
- Recent organ transplant recipient
- Myocardial infarction within 6 months of study
- Anticoagulation (requiring fully therapeutic anticoagulant, not including anti-platelet agents such as aspirin or clopidogrel)
- Blood clotting disorder
- Other implantable devices/ on-demand electronic device
- MRI planned during study period
- Psoriasis, dermatitis, skin infections around ear

### **Screening and Informed Consent**

Patients will be prescreened by study personnel prior to the clinic visit to determine if they meet inclusion and exclusion criteria. **Inclusion criteria:** ≥18 years of age; able to independently consent to participate; plans to undergo elective laparoscopic or open colectomy and/or proctectomy with or without ostomy. **Exclusion criteria:** history of chronic pain disorder (requiring continuous narcotic and/or NSAID use in the week prior to surgery; active opiate abuse; need for regional anesthesia (regional nerve blocks or epidurals); adhesive allergy/sensitivity; history of anxiety disorder on anxiolytics; planned admission to the Intensive Care Unit or prolonged intubation; need for emergent operation; refusal of follow-up phone calls; active pregnancy; history of seizures; on anticoagulation (fully therapeutic anticoagulant, not including anti-platelet agents such as aspirin or clopidogrel); latex allergy; history of implantable devices or on-demand electronic devices; MRI planned during study; recent organ transplant recipient; history of cerebral aneurysm; psoriasis, dermatitis, or skin infections around ear; blood clotting disorder; myocardial infarction within 6 months of study period; use of intraoperative ketamine or lidocaine drips. If a potential participant meets the screening criteria, a member of the study team will explain the study following the regularly scheduled preoperative clinic visit. Once the patient has had their questions answered and agrees to participate, they will sign the informed consent. Patients may require an additional visit to have a thorough discussion of informed consent; this will not be an official clinic visit and the patient and/or insurance will not be billed for the visit. The patient will receive an information sheet about the study with a copy of their informed consent. Consent will be retained by the study coordinator for future records. The patient will undergo all necessary preoperative workup as determined by the primary surgeon.

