After completing the baseline questionnaires explained above, the BRIDGE device will then be placed on the right ear prior to any premedication. The placement of the devices is within standard of care by properly trained medical doctors as already performed as part of separate, ongoing IRB-approved trial at Children's Hospital of Wisconsin (CHW14/208; clinicaltrials.gov # NCT02367729). Training of MDs (Drs. [name], [name], and [name]) will be performed by representatives of Innovative Health Solutions upon IRB protocol approval.

The BRIDGE Surgical kit consists of: (1) An alcohol swab, (2) prep and stay swab, (3) round fixation plasters, (4) fixation plasters to fasten the generator, (5) Steri-strip adhesive vial, (6) Sterile wire harness pack, (7) Generator, (8) Tweezers, (9) Surgical marker, (10)Transilluminator.

1. The neurostimulator placement will be performed as directed and per training protocol instructions identically to current ongoing IRB approved studies at CHW (CHW14/208; clinicaltrials.gov #NCT02367729).
2. Before neurostimulator placement, the subject should be advised that some discomfort is normal at first but should report if the discomfort persists or gets worse after a few minutes. The patients should be advised that they may feel a slight pulsing sensation and perhaps a warming sensation in the ear to which the electrodes are affixed. The pulsing and warming sensation may disappear after approximately 5 minutes. If the discomfort level increases the offending electrode can be slightly repositioned until the patient's discomfort level decreases to an acceptable level. If there is continued discomfort in one specific electrode, it may be removed by cutting the lead.

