The research coordinator (KH) will have the key for unblinding. In an emergency, the PI will also be able to access the key if needed. All other research coordinators, investigators, statisticians and nurses involved will be blinded as to group assignment. The devices will be stored in the manufacturer's packaging and labeled with a serial number and patient ID number. The devices will be stored in a locked office in the Division of Colorectal Surgery, only accessible by research coordinators. Accompanying folders containing all required study materials (VAS, STAI, and PONV score sheets) for each patient will be stored similarly, adjacent to the devices. The unblinded research coordinator (KH) will prepare the subject packages (device and folder) as per randomization scheme. A blinded study team member will bring each subject's numbered package to the pre-operative area when patient arrives on day of surgery. This team member will ask the subject to complete the pre-operative questionnaires and hand the device (numbered with serial # and patient ID only) to one of the certified MDs for placement.

*Intraoperative and Postoperative Protocol*

Neurostimulation will be delivered below sensation threshold continuously for 5 consecutive days, the duration of the device battery. The anesthesiology team will be informed in the preoperative area of participation in the study prior to BRIDGE application. It will be discussed that any use of regional anesthesia or NSAIDs are not permitted in this study. If the anesthesiologist believes the patient has contraindications to other methods of analgesia or anesthesia, or if it may be in the patient's best interest to incorporate regional anesthetic techniques, the patient will be excluded from the study. Operating room staff will be instructed to avoid manipulating the device while moving patient or during procedure. The device does not interfere with any monitoring routinely used in the operating room.

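### The two exclusion lists differ on treated anxiety disorder and ICU admission, and both contain criteria knowable only after allocation, with no defined analysis set to keep those patients in

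*Protocol*

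**What the plan says.** The Protocol carries two exclusion lists, both current text.

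- **Anxiety.** Screening and Informed Consent excludes "history of anxiety disorder on anxiolytics". Exclusion Criteria has no matching item.
- **ICU and intubation.** Exclusion Criteria has "Need for emergent procedure, regional anesthesia (does not include escalation of medical management of pain), admission to ICU" and, as its own bullet, "Prolonged postoperative intubation". Screening and Informed Consent has "planned admission to the Intensive Care Unit or prolonged intubation".
- **Intraoperative infusions.** Both lists carry this item: "Use of intraoperative ketamine or lidocaine drips" in Exclusion Criteria and "use of intraoperative ketamine or lidocaine drips" in Screening and Informed Consent.

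The Day of Surgery section gives the timing. The unblinded coordinator "will prepare the subject packages (device and folder) as per randomization scheme", and the package is then carried to the pre-operative area. After the baseline questionnaires, "the BRIDGE device will then be placed on the right ear prior to any premedication".

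Under Intraoperative and Postoperative Protocol, a patient who needs regional anaesthesia for pain after surgery is taken out of the study at that point. The SAP (Statistical Method) analyses efficacy in an mITT population and adds a per-protocol analysis only if more than 10% of ITT patients fail to qualify for it. It defines neither set.

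**The concern.** There are two separate issues.

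The first is consistency. A candidate with treated anxiety disorder passes one list and fails the other, and so does a patient with an unplanned ICU admission if the unqualified wording is taken literally. Anxiety is measured before surgery and daily afterwards, so whether these patients are enrolled affects whom the results describe.

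The second matters more for inference. Some criteria describe things that happen during or after the operation, when the patient is already allocated and wearing a device. If such patients are removed, the groups compared are no longer the groups randomised. Regional anaesthesia for inadequate pain control is closely tied to the main comparison, total opioid use. ICU admission and prolonged intubation bear on recovery, and so on the Aim 2 outcomes of respiratory depression and length of stay.

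**Working it through.** No figure in the plan is in dispute, so the check is mainly a comparison of passages.

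**1. The two lists side by side**

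| Item | Exclusion Criteria | Screening and Informed Consent | When knowable |
|---|---|---|---|
| Treated anxiety disorder | absent | excluded | before randomisation |
| ICU admission | excluded, unqualified | excluded if planned | planned: before; unplanned: after surgery |
| Prolonged intubation | excluded, described as postoperative | excluded; unclear whether the word planned also governs it | after surgery, unless planned |
| Ketamine or lidocaine drips | excluded | excluded | during surgery |
| Regional anaesthesia | excluded | excluded | before, during or after surgery |

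The lists differ on the first three rows. On ketamine or lidocaine they agree, and both have the timing problem.

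**2. Timing.** The package follows the randomisation scheme before it reaches the patient, and the device goes on before premedication. Anything first known in the operating room or later is therefore known after allocation and after device placement.

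**3. Are these criteria applied after surgery?** For regional anaesthesia, yes: the postoperative text says so. That item shares a bullet with ICU admission. The bullet's own exception for escalated medical pain management also fits the postoperative period, where escalation of the oral regimen is said not to lead to exclusion. For ICU admission and intubation, the documents do not say.

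**4. Does the SAP settle it?** No. With mITT undefined, these patients may be in or out of the primary analysis.

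**5. Size.** The SAP's own numbers reproduce: 25 / (1 - 0.10) = 27.8, so 28 per group and 56 in all. The allowance covers 28 - 25 = 3 losses per group. The documents give no rate for any of these events, so everything below is assumption.

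- Anxiety: if 10-20% of candidates were affected, 56 x 0.10 = 5.6 to 56 x 0.20 = 11.2, or about 6-11 enrolments, would depend on the list used.
- Unplanned ICU admission or prolonged intubation: at 2-5%, 56 x 0.02 = 1.1 to 56 x 0.05 = 2.8, or about 1-3 patients.
- Post-randomisation removals at rate r on top of 10% dropout leave 28 x 0.90 x (1 - r) per group; keeping 25 needs 25 / [0.90 x (1 - r)].

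| Assumed r | Left per group | Needed per group |
|---|---|---|
| 5% | 23.9 | 30 |
| 10% | 22.7 | 31 |
| 20% | 20.2 | 35 |

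- Bias: if a fraction p of a group is removed and the mean log opioid use of those removed exceeds that of those kept by D, the kept mean is too low by p x D. The between-group bias is the difference in p x D, and is zero if the groups match. As an extreme illustration, take 1 or 3 removals, all from one group of 28, with D equal to the SAP's SD of 0.58: 1/28 x 0.58 = 0.021 and 3/28 x 0.58 = 0.062. The SAP's 2.3 fits base 10 (log10 of 180 = 2.26), so these are factors of 10^0.021 = 1.05 and 10^0.062 = 1.15. That is a distortion of about 5% to 15%, against a planned reduction of 25%.

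**The case against.** Much of the other side's case stands.

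- A reader might infer that staff cannot apply both lists, or that the enrolled population is undetermined. The documents do not support that. Both are exclusion lists, and anyone meeting either can be excluded.
- A reader might infer that the anxiety discrepancy biases the result. It acts before randomisation and affects both groups alike. It bears on eligibility, generalisability and perhaps variance.
- The opening words of the ICU bullet may mean a need foreseen at screening, and the other list's qualifier favours that reading. No passage states that a randomised patient is removed for unplanned ICU admission or prolonged intubation. Complications are collected by Clavien-Dindo grade, which suggests that such patients stay under observation.
- A reader might place the timing fault in the Exclusion Criteria list alone. It is not confined there: ketamine or lidocaine is in both lists, and the explicit postoperative removal is in the postoperative text.
- Patients, device placers, investigators, nurses and statisticians are blinded. This limits selective removal, but it does not help if the treatment itself changes who needs regional anaesthesia or recovers poorly.

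The objection does not remove the explicit postoperative exclusion for regional anaesthesia, the intraoperative criterion in both lists, or the undefined mITT set.

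**Conclusion.** The point holds in two parts. The lists differ on treated anxiety disorder and on the ICU and intubation wording; this is an eligibility inconsistency and not a source of bias between groups. Separately, criteria knowable only after allocation and device placement appear in both lists, one postoperative exclusion is explicit, and the SAP leaves the handling of these patients open. That creates a risk of bias in the opioid comparison.

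The size cannot be derived from the documents. It depends on how many patients are removed, how unevenly, and how different they are; balanced removal of similar patients would cause none. A reader might conclude that the comparison is broken or that patients are certainly dropped on outcome, but the text shows only that this may happen. Two assumptions remain: that allocation precedes arrival in the pre-operative area, inferred from how packages are prepared, and that the ICU item could be read to cover unplanned admission.

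**What to change.** 1. Reconcile Exclusion Criteria with Screening and Informed Consent into one screening list. The sponsor decides whether treated anxiety disorder is excluded.
2. Restrict eligibility exclusions to facts known before randomisation, for example planned ICU admission or planned prolonged intubation, and state that the qualifier covers both.
3. In the SAP, define the primary mITT set as all randomised patients who received a device, analysed as allocated. Record unplanned ICU admission, prolonged intubation, ketamine or lidocaine use and regional anaesthesia as complications, protocol deviations or rescue, as applicable. The Data Collection section already lists complications and the need for regional anaesthesia as a rescue method, so the postoperative exclusion text must be reconciled with it. This concerns data and analysis only, not what care such a patient should receive.
4. Confine removal for these events to a defined per-protocol set. Under the SAP's existing trigger (0.10 x 56 = 5.6), that analysis would run only if 6 or more of 56 patients fail to qualify.

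The cost is wording in both documents. In-hospital opioid totals come from the medical record, so little extra collection is needed. The downside is that a few atypical patients stay in and add some variance, and the opioid total of a patient given regional anaesthesia will partly reflect that rescue.

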### **Day of Surgery/First Day of Participation**

Upon presentation to the preoperative staging area on the day of surgery, subjects will first be asked by a member of the study team to rate their pain (VAS scale), anxiety (STAI scale), and nausea (PONV scale). The Visual Analog Scale (VAS) is a nearly universal score which rates patients' pain on a scale of 0-10. This scale has been well studied and has been employed by both participating institutions as the primary grading system for pain.(1,2) Anxiety will be measured with the State-Trait Anxiety Inventory (STAI), originally published in 1970 as a method to evaluate current anxiety (state anxiety) as well as propensity to become anxious (trait anxiety).(3) The postoperative nausea vomiting (PONV) scale has been shown to be a reliable measure of nausea, and has also been used at both participating institutions.(4) The patients will also submit a blood sample and buccal swab prior to surgery. As standard of care, a urine pregnancy test is a routine preoperative lab for all females of childbearing age. As such, this test will be performed on the morning of surgery.

*Auricular Neurostimulation Details and Application:*

This protocol has been generously shared by our colleagues at CHW, based on an ongoing, IRB-approved trial (CHW14/208; clinicaltrials.gov # NCT02367729). It has been adapted to fit our patient population. The BRIDGE is an FDA-approved (510(k)140530) and commercially available device manufactured by Key Electronics (Jeffersonville, IN, USA) and distributed by Innovative Health Solutions (Versailles, IN, USA). BRIDGE is an ambulatory, neurological device which consists of a battery powered, externally affixed generator with 4 wire leads attached to 3 electrode/needle arrays and one single point needle. The arrays are designed to produce a field effect similar to surgically implanted peripheral neurostimulators. One BRIDGE device per patient will be used in this study.

After completing the baseline questionnaires explained above, the BRIDGE device will then be placed on the right ear prior to any premedication. The placement of the devices is within standard of care by properly trained medical doctors as already performed as part of separate, ongoing IRB-approved trial at Children's Hospital of Wisconsin (CHW14/208; clinicaltrials.gov # NCT02367729). Training of MDs (Drs. [name], [name], and [name]) will be performed by representatives of Innovative Health Solutions upon IRB protocol approval.

The BRIDGE Surgical kit consists of: (1) An alcohol swab, (2) prep and stay swab, (3) round fixation plasters, (4) fixation plasters to fasten the generator, (5) Steri-strip adhesive vial, (6) Sterile wire harness pack, (7) Generator, (8) Tweezers, (9) Surgical marker, (10)Transilluminator.

1. The neurostimulator placement will be performed as directed and per training protocol instructions identically to current ongoing IRB approved studies at CHW (CHW14/208; clinicaltrials.gov #NCT02367729).
2. Before neurostimulator placement, the subject should be advised that some discomfort is normal at first but should report if the discomfort persists or gets worse after a few minutes. The patients should be advised that they may feel a slight pulsing sensation and perhaps a warming sensation in the ear to which the electrodes are affixed. The pulsing and warming sensation may disappear after approximately 5 minutes. If the discomfort level increases the offending electrode can be slightly repositioned until the patient's discomfort level decreases to an acceptable level. If there is continued discomfort in one specific electrode, it may be removed by cutting the lead.
3. The electrodes will be placed percutaneously in the external ear with the help of a transilluminator to visualize the neurovascular bundles. Three electrodes will be placed on the ventral and one on the dorsal aspect of the ear. The exact location of the implantation may vary slightly from person to person but is determined by both knowledge of auricular neuro-anatomy and visualization of the neurovascular bundles by transillumination. The electrodes will be taped and secured behind the ear next to the generator itself which is secured to the skin with adhesive. The placement of the devices is within standard of care by properly trained medical doctors as already performed as part of separate, ongoing IRB-approved trial at CHW (CHW14/208; clinicaltrials.gov #NCT02367729).
4. The device will then be activated. Sham devices will appear to be activated, though will not cause neurostimulation, in order to maintain impartiality of the investigators as the status of the device will not be apparent.

5. Device placement will take approximately 5 minutes. The patient will remain at rest for the next 5 minutes in the pre-operative area. Care will be taken not to interfere with standard pre-operative procedures.
6. Patients will be advised not to manipulate the device or immerse the device in water as it is water resistant but not water proof. If showering or washing hair, they should place a dry wash cloth or plastic covering over the area to protect the device.

*Randomization Protocol, Material Storage, and Blinding*

Subjects will be randomized in a 1:1 ratio to either active or inactive group. Randomization will be determined using a computer program based on random number generation in blocks of 10 subjects at a time. The manufacturer will provide the researchers with one device per package and each package will have a serial number. The inactive devices will be custom-made by the physical manufacturer, Key Electronics, Jeffersonville, IN, and will be identical in every way to the active device except it will lack the battery. The devices will be "made to order" when requested by the PI and will be shipped and packaged as above. Both the subjects and the doctors placing the devices will be blinded, as the active and inactive devices will look identical with identical packaging and placement procedures.

The research coordinator (KH) will have the key for unblinding. In an emergency, the PI will also be able to access the key if needed. All other research coordinators, investigators, statisticians and nurses involved will be blinded as to group assignment. The devices will be stored in the manufacturer's packaging and labeled with a serial number and patient ID number. The devices will be stored in a locked office in the Division of Colorectal Surgery, only accessible by research coordinators. Accompanying folders containing all required study materials (VAS, STAI, and PONV score sheets) for each patient will be stored similarly, adjacent to the devices. The unblinded research coordinator (KH) will prepare the subject packages (device and folder) as per randomization scheme. A blinded study team member will bring each subject's numbered package to the pre-operative area when patient arrives on day of surgery. This team member will ask the subject to complete the pre-operative questionnaires and hand the device (numbered with serial # and patient ID only) to one of the certified MDs for placement.

*Intraoperative and Postoperative Protocol*

Neurostimulation will be delivered below sensation threshold continuously for 5 consecutive days, the duration of the device battery. The anesthesiology team will be informed in the preoperative area of participation in the study prior to BRIDGE application. It will be discussed that any use of regional anesthesia or NSAIDs are not permitted in this study. If the anesthesiologist believes the patient has contraindications to other methods of analgesia or anesthesia, or if it may be in the patient's best interest to incorporate regional anesthetic techniques, the patient will be excluded from the study. Operating room staff will be instructed to avoid manipulating the device while moving patient or during procedure. The device does not interfere with any monitoring routinely used in the operating room.

The patient will undergo general anesthesia per standard of care. There will be no intraoperative or postoperative use of nonsteroidal anti-inflammatory medications (NSAIDs) (i.e. ketorolac, ibuprofen, diclofenac) or regional pain therapies (i.e. epidural anesthesia, transversus abdominis plan blocks); anesthetic plan will otherwise be per treating physician. Once the procedure is over and the patient is extubated and transferred to the postoperative care unit, the patient will continue to receive postoperative pain control per standard of care, as determined by the anesthesia and surgical teams. Auricular neurostimulation has been postulated to decrease the inflammatory response. As NSAIDs (Non-steroidal anti-inflammatory drugs) have a direct inhibitory effect on the inflammatory response, the use of these medications would have a variable effect on the measurement of inflammatory markers and the biological response to surgery. Additionally, NSAIDs are known to have an analgesic effect, which will confound the primary outcome - opioid medication use. Acetaminophen has a benign side effect profile, so the majority will have this included in their regimen. However, NSAIDs have significant risks of kidney injury and bleeding and a large proportion of patients are not eligible. While this would be ideally be randomly distributed between groups; however, in such small study there is risk of imbalanced use that could

further confound our results. Therefore, the postoperative pain regimen will remain standardized for all patients: hydromorphone PCA (no basal rate) while NPO, oxycodone 5-10mg PO q6h PRN once tolerating a diet, and acetaminophen PRN as determined by the primary team.

The nurses caring for the patient during the recovery period after surgery will be alerted to the patient's participation in the study. The immediate postoperative recovery nurse will be alerted by a member of the surgical team upon patient arrival to the post-anesthesia care unit. Once the patient is transferred to the hospital floor, a sign will be placed on the door to the patient's room indicating that they are participating in the study. This sign will include minimal information about the study, along with contact information for study personnel and will not include any identifying health or personal information. Nurses will be encouraged to contact the study team with concerns. While having a sign on the door does compromise some confidentiality, this is routinely performed for research purposes throughout the hospital. Due to the numerous teams caring for surgical patients, as well as the frequent RN shift changes, it is necessary to alert all caregivers about study participation, as protocol violations will jeopardize the integrity of the data. A more detailed sign will be posted in the RN workroom while a patient actively enrolled in the study is on the unit. This will allow a further description of the study in order to maintain confidentiality as well as integrity of data.

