#### Data Collection

The following data will be extracted from the medical record:

- Surgical data:
  - Type of colon resection (right, left, sigmoid, total, etc.)
  - Operative technique (laparoscopic, hand-assisted, robotic, open)
  - Presence and type of ostomy, if applicable
- Demographics: age, sex, comorbidities, previous symptoms, diagnosis, indication for operation
- Total daily dosage of narcotics during hospitalization (milligrams of hydromorphone, converted to morphine equivalents), including intraoperative narcotics
- VAS scores (daily maximum and AUC)
- Number of emeses
- Laboratory values (if ordered by primary team)
- Respiratory depression, determined by need for opioid reversal agent (naloxone)
- Rescue methods for pain control (need for pain team consult, need for regional anesthesia)
- Complications (per Clavien-Dindo Classification)
- Return of bowel function (time to first flatus, time to first bowel movement)
  - Postoperative ileus, determined by need for NG tube insertion
- Length of stay (in days, including day of surgery)
- Rate of readmission
- Patient satisfaction scores
- Discharge destination (i.e. home, skilled nursing facility)
- Incidence of withdrawal (i.e. patients requesting to terminate study/remove device) and reason
- Need for additional narcotic prescription refills after discharge

The following data are study-specific and will be collected by the study personnel:

- STAI, and PONV scores during 5 day life of BRIDGE device, at a minimum once daily
- Need for device modification or removal, if applicable

- Biospecimens. Samples will be immediately de-identified after collection and coded with the study ID number. They will be stored in the Divisions research facilities de-identified for analysis.
- VAS, STAI, and PONV scores at first follow-up appointment as well as device day 30
- Device-specific survey

  

1. Bijur, P.E., W. Silver, and E.J. Gallagher, Reliability of the visual analog scale for measurement of acute pain. *Acad Emerg Med*, 2001. 8(12): p. 1153-7.
2. Scott, J. and E.C. Huskisson, Graphic representation of pain. *Pain*, 1976. 2(2): p. 175-84.
3. Julian, L.J., Measures of anxiety: State-Trait Anxiety Inventory (STAI), Beck Anxiety Inventory (BAI), and Hospital Anxiety and Depression Scale-Anxiety (HADS-A). *Arthritis Care Res (Hoboken)*, 2011. 63 Suppl 11: p. S467-72.

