Summary statistics such as mean, median, standard deviation, range and correlation plots and tree analysis will be used to examine distributions and interrelationships. Where necessary, for parametric assumption, we will employ appropriate transformations with justifications and compare using Student's t-test. If data cannot be appropriately transformed, we will compare variables between the two groups using a Mann-Whitney test. Pain scores will be analyzed using area under the curve for the entire hospitalization.

Categorical variables

We will compare the two groups using a chi - square or Fisher-Haltom exact test.

Power

For the efficacy outcomes, the main comparison of interest is total hospital narcotic requirement in oral morphine equivalents. For simplicity in power calculations, we use a (conservative) two sample two-sided t-test at an alpha of 0.05 on the change. For a power of 90%, assuming a 25% decrease in narcotic consumption with an average total hospital narcotic consumption of 180 mEq oral morphine log-transformed for normal distribution to 2.3 with standard deviation of 0.58, we would require 25 patients per group. Assuming a dropout rate of 10%, we estimate 28 participants in each group will be needed.

Safety Data

All safety variables (e.g., adverse events) will be summarized for each group (including follow-up) using descriptive statistics. Incidence of adverse events will be summarized by treatment.

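### Planned surgical approach is neither a stratification factor nor an analysis covariate; adjusting for it would give a modest, cheap gain in precision and interpretability

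*Protocol*

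**What the plan says.** The eligible operations are mixed (Protocol, Inclusion Criteria): "Plans for elective laparoscopic or open colectomy or proctectomy with or without ostomy". Allocation is 1:1 (Protocol, Randomization Protocol, Material Storage, and Blinding): "Randomization will be determined using a computer program based on random number generation in blocks of 10 subjects at a time". No stratification factor is named.

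The protocol lists among the items extracted from the medical record (Protocol, Data Collection) "Operative technique (laparoscopic, hand-assisted, robotic, open". It lists no separate field for the approach planned before allocation.

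The SAP (Statistical Method) gives approach no role in the comparisons. Continuous and ordinal outcomes get a t-test after transformation, or a Mann-Whitney test; categorical outcomes get a chi-square or exact test. Correlation plots and tree analysis are mentioned only for looking at distributions and interrelationships.

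The sample size (SAP, Power) rests on these statements: "For a power of 90%, assuming a 25% decrease in narcotic consumption", a mean of "180 mEq oral morphine log-transformed for normal distribution to 2.3 with standard deviation of 0.58", then "we would require 25 patients per group" and "Assuming a dropout rate of 10%, we estimate 28 participants in each group will be needed".

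**The concern.** Approach is a baseline feature that plausibly influences every Aim 1 and Aim 2 outcome. If one arm happens to receive more open operations, opioid use, pain, ileus and stay may all move in the same direction. Agreement across those outcomes would then not be independent support for a device effect. Variation between approaches also sits in the error term of each unadjusted comparison.

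The protocol accepts this kind of reasoning elsewhere. In Intraoperative and Postoperative Protocol, part of its case for barring NSAIDs is that chance may not balance their use in a study this small. Planned approach can be balanced, or adjusted for, without restricting anyone's care.

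**Working it through.** **Inputs from the documents.** Two-sided alpha 0.05, power 90%, mean 180 (logged to 2.3, so base 10), SD 0.58, 25 per group, 10% dropout, 28 per group (56 in total), blocks of 10.

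**Inputs assumed, because the documents give none.** Share of open operations 20%, 30% or 50%; opioid use in open relative to minimally invasive surgery 1.5, 2 or 3 times.

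**1. The plan's own figure.** Taking 25% off the logged mean gives δ = 0.25 × 2.3 = 0.575. The normal approximation is n = 2(1.960 + 1.282)² × (0.58/0.575)² = 21.4, so 22 per group. The exact t-test gives 23, or 24 with δ = 0.25 × log10(180) = 0.25 × 2.255 = 0.564. Both are close to the stated 25. Dropout: 25/0.9 = 27.8, so 28.

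There are therefore two yardsticks. The δ that reproduces the sample size is 0.575 log10, a cut of 1 − 10^(−0.575) = 73%. A literal 25% cut is |log10(0.75)| = 0.125 log10.

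**2. From imbalance to shift.** Shift in mean log10 opioid = gap in the open share × log10(ratio). The logs are 0.176, 0.301 and 0.477 for ratios 1.5, 2 and 3. The gap needed is:
- for half a literal 25% cut (0.0625): 0.36, 0.21 and 0.13;
- for a full one (0.125): 0.71, 0.42 and 0.26;
- for 0.575, even at ratio 3: 0.575/0.477 = 1.21. A gap cannot exceed 1, so this cannot happen. The ratio would have to exceed 10^0.575 = 3.76.

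**3. How often.** 20,000 simulated trials per case mix, 56 patients, permuted blocks of 10. Gaps are absolute, so only about half would favour the device.

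| Open share (assumed) | SD of gap | 95th percentile of gap | Gap ≥ 20 points | Shift ≥ 0.0625, ratio 2 / 3 | Shift ≥ 0.125, ratio 2 / 3 |
|---|---|---|---|---|---|
| 20% | 0.11 | 21 points | 6% | 6% / 22% | 0% / 1.4% |
| 30% | 0.12 | 24 points | 10% | 9% / 28% | 0.04% / 3.3% |
| 50% | 0.13 | 25 points | 14% | 14% / 34% | 0.2% / 4.4% |

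At ratio 1.5 the shift reaches 0.0625 in at most about 1% of trials and never reached 0.125.

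**4. Share of variance.** With half open, share = 0.25 × log10(ratio)² / 0.58² = 2%, 7% and 17% for ratios 1.5, 2 and 3.

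**5. Effect of adjusting.** 4,000 simulated trials per setting, total SD held at 0.58. Power is shown for 50 patients, half open.

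| Ratio | Power at δ = 0.575, unadjusted → adjusted | Power at δ = 0.125, unadjusted → adjusted |
|---|---|---|
| 1.5 | 0.924 → 0.923 | 0.116 → 0.115 |
| 2 | 0.931 → 0.944 | 0.124 → 0.127 |
| 3 | 0.933 → 0.959 | 0.113 → 0.128 |

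Type I error over all settings run (50 or 56 patients, 30% or 50% open, ratios up to 4) was 0.042 to 0.058 unadjusted and 0.045 to 0.058 adjusted: about 5% either way, within simulation error.

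**6. What one imbalanced trial looks like.** Take a gap of 6/28 = 0.214 and no device effect. The shift is 0.065 (ratio 2) or 0.102 (ratio 3), against a standard error of 0.58 × √(2/28) = 0.155. That is 0.42 or 0.66 standard errors. By normal approximation, the unadjusted test then rejects about 7% or 10% of the time, against 5% on average over all allocations.

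**The case against.** The strongest case against acting is that randomisation already does its job. Chance imbalance is part of the 5% error, and if the SD of 0.58 came from a mixed population (not stated), variation due to approach is already in the sample size. The power gain from adjusting is nil at a ratio of 1.5 and small at 2 or 3. The prognostic effect of approach is not in the documents. Baseline characteristics will be summarised and technique extracted, so an imbalance would be visible. The NSAID parallel is imperfect: NSAID use arises after randomisation and can be barred, whereas approach is a baseline feature balanced in expectation. Nor is approach the only candidate: colectomy versus proctectomy, ostomy and institution could be argued too.

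Most of this stands, and it limits the point to a modest improvement. It does not remove it. Seeing an imbalance without a prespecified adjusted analysis leaves only a post hoc one. The other factors are a reason to choose deliberately, since 56 patients cannot support stratifying on all of them.

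A reader might infer that imbalance in approach could rival the effect sought. The figures do not support that. A shift equal to a literal 25% cut needs about a threefold opioid ratio and then occurs in only about 1% to 4% of trials; the 0.575 behind the sample size is out of reach at the ratios considered.

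**Conclusion.** The point holds as a precision and interpretability issue. Approach is known before allocation, is plausibly prognostic, and is used in neither the randomisation nor the analysis. Gaps of 20 points or more are not rare (about 6% to 14% of trials). They can shift the result by a material part of a literal 25% reduction if open surgery at least doubles opioid use. The case mix and opioid ratios are assumptions.

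A reader might also infer that the unstratified design biases the comparison or invalidates the test. It does neither: type I error stays near 5%.

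The need for two yardsticks comes from a separate and larger problem in the SAP's Power section. There, 25% appears to have been taken off the logged mean. Adjusting for approach does not solve that: power for a literal 25% cut stays near 12% at 25 per group.

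**What to change.** Record planned approach (open versus minimally invasive) before allocation, and state where hand-assisted and robotic operations fall. Prespecify planned approach as a factor in the Aim 1 and Aim 2 comparisons: ANCOVA on the transformed scale, or a stratified rank test where no transformation serves. Use the planned approach, not the performed one, because conversion happens after the device is placed.

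If randomisation has not begun, also stratify the list by planned approach, with smaller blocks (for example 4 or 6), and keep the factor in the analysis. If it has begun, adjust only.

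Cost: one extra recorded field, one degree of freedom and a short addition to the SAP. Stratifying adds a second list for the coordinator who already prepares the packages, and possibly an incomplete block in each stratum.
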